7.2 Method of Treatment Assignment

All participants will be randomized via a random allocation to alvelestat or placebo arms to meet enrolment needs of the study. The randomization numbers will be linked to the 2 treatment regimens, and the randomization scheme will not be stratified

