10.3.2 Efficacy Analyses (Secondary Endpoints)

Comparison of alvelestat and placebo will be performed using an analysis of covariance (ANCOVA) model for continuous variables, with Least Squared means for the difference between pairwise treatment regimens, standard errors, two-sided 95% CIs and P-value for the difference between pairwise treatment regimens.

Categorical variable will be compared between treatments by Chi-square test (or Fisher's exact test as appropriate).

Endpoint	Statistical Analysis Methods
Biomarkers	
Within individual absolute and % change from baseline will be calculated. An analysis of covariance (ANCOVA) model with baseline levels as a covariate and treatment strata as factors will be used to generate least squared means and least squared mean differences between treatment groups. Continuous measures will be log transformed where appropriate.
 
The parameters during treatment will be compared to the baseline values for active and placebo patients separately to evaluate natural variability of the markers.
 
The time-matched biomarker values will be compared between placebo and active groups to assess the differences outside natural variability and time to significant change for the responsive biomarkers.

SaO ₂ /FiO ₂	Within individual absolute and % change from baseline will be calculated.
Disease progression (alive and respiratory failure free)	The proportion alive and respiratory failure free will be presented by the number of observations, absolute and relative (%) frequency.

Endpoint	Statistical Analysis Methods
Other clinical outcomes	
Continuous variables (e.g. duration of hospital/ICU stay) mean, standard deviation, minimum, maximum, median, lower quartile, and upper quartile).
 
Change in level of respiratory support will be presented as shift tables.
 
Time to event (e.g. time to room air, to death, to discharge), will be analysed using Kaplan-Meier methods, and quartiles for the median time to event will be presented together with their 95% confidence intervals. Comparisons between treatment regimens will be performed by means of the log-rank test.

Disease severity (WHO 9-point ordinal scale)	
Change from baseline will be presented as mean, standard deviation, minimum, maximum, median, lower quartile, and upper quartile).
 
Responder analyses (improvement and deterioration) will be presented as number of observations, absolute and relative (%) frequency.

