5.3.1 Inclusion Criteria

- Male or Female
- Age ≥ 18 years
- Proven SARS-CoV-2 infection (confirmed by PCR from a nasopharyngeal or lower respiratory tract sample)
- A score of Grade 3 to 5 on the WHO 9-point Ordinal Scale
- Male participants must agree to use a highly effective contraception
- Female participants are eligible to participate if not pregnant; not breastfeeding; and at least one of the following conditions is met:
 - Not a woman of childbearing potential
 - OR
 - A woman of childbearing potential who agrees to follow the contraceptive

guidance during the treatment phase and for at least 4 days after the last dose of study medication

- Capable of giving signed informed consent which includes a commitment to comply with the requirements and restrictions listed in the informed consent form (ICF) and within this protocol.

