- Change from baseline in desmosine/isodesmosine will be compared between treatments using ANCOVA models with treatment allocation as a factor and baseline desmosine/isodesmosine as a covariate. Estimated treatment difference with 95% confidence intervals and associated 2-sided p-value will be given.
- Biomarker values that are below the lower limit of quantitation of assay will be reported as the lower limit of quantitation (LLQ)/2.
- Biomarker values may be log transformed if appropriate.

The proportion of patients with recovery at Day 29 will be compared between treatment groups using a logistic regression model adjusting for treatment and COVID disease severity. The difference between treatment arms will be expressed as a difference in proportions as measured by the Cochran Mantel-Haenzel (stratum)-weighted estimator based on the fitted logistic regression model. The delta method will be used to calculate the standard error for the difference and the associated confidence interval [Ge, 2011]. In addition, the raw proportions per treatment group will be given. If 0 events in any of the groups only raw proportions will be given.

Summaries of the results of the secondary analysis for recovery are displayed in Table 10.

Table 10. COSTA analysis tables – Secondary Analysis (Recovery)

Table #	Table Name	Table Contents
	Proportion of Patients with Recovery at 29 Days, ITT	Overall and by Treatment Group 
 • By Age Group • By Sex • By COVID Disease Severity
	Proportion of Patients with Recovery at 29 Days, PP	Overall and by Treatment Group

Patients that die in the study will be handled as worst case in all analyses.

To have an evaluation using all patients we will count an event as the type of need or worse (e.g., patients with oxygen need; non-invasive ventilator need; ventilator need; or with death at time of evaluation will be counted as having data supporting oxygen need), and included in both denominator and numerator.

8.4.1 Time to a recovery state (Day 1 - Day 29; measured in days)

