8.4.2.1 Sub-sets based on post-randomization outcome

Descriptive summaries of the proportion of patients as well as the duration of the worsening following initiation of study medication will be provided for these endpoints:

- Proportion of patients needing re-hospitalization (post-dose Day 1 – Day 60).
 - Applies to the sub-set of patients that were randomized, treated with study medication and discharged from the hospital alive then re-admitted to the hospital for COVID-19 related treatment.
- Proportion of patients and duration of new oxygen use (post-dose Day 1 - Day 29; measured in days).
 - Applies to the sub-set of patients that were randomized and treated with study medication but then had a new need for supplemental oxygen (score worsened to 4, 5 or 6).
 - Or those which improved during hospitalization (to 3) and then their clinical status worsened again (to 4, 5 or 6).
- Proportion of patients and duration of new non-invasive ventilation or high flow oxygen use (post-dose Day 1 - Day 29; measured in days).

- Applies to the sub-set of alive patients that were randomized and treated with study medication but then had a new need for non-invasive ventilation or high-flow oxygen use (score worsened to 5 or 6).
- Or those which improved during hospitalization (to 3 or 4) and then their clinical status worsened again (to 5 or 6)

The total number of days with recorded use will be the sum of all reported days, regardless of whether the days occur consecutively or in disjoint intervals.

8.4.3 Change from baseline in WHO ordinal scale (Days 10 and 29).

Change from baseline in WHO ordinal scale will be compared between treatments using ANCOVA models with treatment allocation as a factor and baseline WHO score as a covariate. Estimated treatment difference with 95% confidence intervals and associated 2-sided p-value will be given.

8.4.4 Total time on supplemental oxygen (Day 1 - Day 29; measured in days).

The total number of days with recorded use will be the sum of all reported days, regardless of whether the days occur consecutively or in disjoint intervals. Results will be summarized by descriptive statistics including medians and quartiles by treatment arm and compared between treatment groups using Wilcoxon rank sum test. Patients that do not reach the specified score on any day will be counted as 0 days.

8.4.5 Total time on non-invasive ventilator use (Day 1 - Day 29; measured in days).

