8.4.6 Duration of hospitalization (Day 1 - Day 29; measured in days)

The total number of days with recorded use will be the sum of all reported days, regardless of whether the days occur consecutively or in disjoint intervals. Results will be summarized by descriptive statistics including medians and quartiles by treatment arm and compared between treatment groups using Wilcoxon rank sum test.

Summaries of the results of the secondary analyses are displayed in Table 11.

Table 11. COSTA analysis tables - Secondary Analyses.

Table #	Table Name	Table Contents
	Time to recovery, Day 1 - Day 29	Overall and by Treatment group
	Proportion of patients in recovery at Day 60, ITT	Overall and by Treatment group Day 1 – Day 10 Day 1 – Day 60
	Proportion of patients with improvement of one category using the WHO ordinal scale from Day 1, ITT	Overall and by Treatment group Day 1 – Day 10 Day 1 – Day 29
	Proportion of patients with improvement of two categories using the WHO ordinal scale from Day 1, ITT	Overall and by Treatment group Day 1 – Day 10 Day 1 – Day 29
	All-cause mortality, ITT	Overall and by Treatment group At Day 29 At Day 60

Table #	Table Name	Table Contents
	Proportion of patients alive and not in respiratory failure (invasive mechanical ventilation or extracorporeal membrane oxygenation (ECMO) at Day 29, ITT	At Day 90 Overall and by Treatment group Day 1 – Day 10 Day 1 – Day 29
	Summary of the proportion of patients re-hospitalized following initiation of study medication and subsequent discharge (over 60 days), ITT	Overall and by Treatment group
	Duration of hospitalization from Day 1 (Day 1 - Day 29; measured in days), ITT	Overall and by Treatment group
	Change from baseline WHO ordinal scale at Days 10 and 29, ITT	Overall and by Treatment group Baseline – Day 10 Baseline – Day 29
	Total time on supplemental oxygen (Day 1 - Day 29; measured in days), ITT	Overall and by Treatment group
	Total time of non-invasive ventilation or high flow oxygen use (post-dose Day 1 - Day 29; measured in days).	Overall and by Treatment group
	Summary of the proportion of patients with oxygen use at Days 10 and 29, ITT	Overall and by Treatment group
	Summary of the proportion of patients with non-invasive ventilation or high flow oxygen use at Days 10 and 29, ITT	Overall and by Treatment group

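### Oxygen, ventilator and hospital days are compared by unadjusted Wilcoxon tests, although baseline WHO score is available and adjusting for it would cost almost nothing

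*SAP*

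**What the plan says.** SAP 8.4.4 (oxygen days), 8.4.5 (non-invasive ventilator days) and 8.4.6 (hospital days), each over Day 1 to Day 29, use the same sentence: "Results will be summarized by descriptive statistics including medians and quartiles by treatment arm and compared between treatment groups using Wilcoxon rank sum test". None names a covariate or a stratum.

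Entry requires "A score of Grade 3 to 5 on the WHO 9-point Ordinal Scale". On that scale 3 is no oxygen, 4 is mask or prongs, and 5 is non-invasive ventilation or high-flow oxygen. The score is recorded on Day 1 (protocol section 2.0).

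Other analyses in the plan do adjust:
- SAP 8.4.3 analyses change in WHO score with "ANCOVA models with treatment allocation as a factor and baseline WHO score as a covariate".
- SAP 8.4 analyses Day 29 recovery "using a logistic regression model adjusting for treatment and COVID disease severity".
- Protocol 10.3.2 states as its general rule: "Comparison of alvelestat and placebo will be performed using an analysis of covariance (ANCOVA) model for continuous variables".

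Protocol 7.2 says that "the randomization scheme will not be stratified". SAP 7.4 scores patients who die as worst case. The trial has 15 patients and is not powered for any endpoint, and its efficacy analyses are exploratory (protocol 10.1, SAP 7.2).

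**The concern.** For oxygen and ventilator days, the entry score overlaps with the outcome. The totals start on Day 1. A patient who enters at WHO 3 has no oxygen day yet, while one who enters at 4 or 5 is already accruing them. For non-invasive ventilation or high flow, only WHO 5 patients start counting at once. The argument is weaker for hospital days, because every patient at WHO 3 to 5 is in hospital on Day 1.

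A test that ignores a predictive baseline variable leaves its variance in the comparison. With unstratified allocation of 15 patients, it also lets a chance difference in entry status carry into the estimated effect. The SAP gives no reason for omitting the score here. At stake are the precision and readability of three exploratory comparisons that may inform later studies.

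**Working it through.** **Reference figure.** The plan states no power, effect size or SD for these endpoints, so there is no figure to reproduce.

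**Inputs from the documents.** N = 15; two-sided 5% tests; baseline score 3, 4 or 5; a 29-day window; deaths scored worst case. Allocation is 10:5 in the protocol but 7-8 per arm in the SAP, so 10:5 and 8:7 were both run.

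**Assumed inputs.** The drug multiplies mean days by 0.5. Entry mix is 20/50/30% at WHO 3/4/5. Days are log-normal, rounded and capped at 29, with the means and coefficient of variation (CV) shown. There is no dropout. Where deaths are included, their probability is 2/8/20% by score and they count as 29 days.

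**Step 1: power by simulation.** Unadjusted exact Wilcoxon against rank ANCOVA on baseline WHO score with a permutation p-value. R² is the share of rank variance in days explained by the score when there is no drug effect.

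| Assumed mean days at WHO 3/4/5, CV | R² | 10:5 power (%) | 8:7 power (%) |
|---|---|---|---|
| Hospital 5/6/8, 0.6 | 0.14 | 47.8 → 49.3 | 52.3 → 53.7 |
| Hospital 4/6/10, 0.8 | 0.22 | 29.4 → 33.2 | 32.6 → 35.7 |
| Hospital 4/7/14, 1.0 | 0.25 | 20.8 → 24.6 | 24.4 → 27.4 |
| Same, with deaths | 0.26 | 14.2 → 17.1 | 17.2 → 20.4 |
| Hospital 4/7/14, 0.8 | 0.31 | 27.0 → 34.9 | 29.2 → 36.3 |
| Oxygen 1/5/11, 1.0 | 0.44 | 15.8 → 23.2 | 17.3 → 25.6 |
| Same, with deaths | 0.44 | 10.8 → 15.8 | 13.1 → 19.0 |
| Oxygen 0.5/5/12, 0.6 | 0.64 | 19 → 40 | 19.4 → 44.4 |
| Ventilator 0/0.5/5, 0.8 | 0.65 | 8 → 17 | 7.4 → 15.2 |

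Rejection under the null was about 4 to 6% for all tests. Two further 10:5 results show the spread: a moderate link (R² 0.40) with narrower variation gave 34 → 49, and another moderate-link scenario with deaths gave 18 → 26. A separate run at 10:5 with other assumed durations gave 17 → 26 for oxygen days, 10 → 14 with deaths, 5 → 8 for ventilator days and 30 → 32 for hospital days.

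**Step 2: formula check on the log scale.** Power ≈ Φ(δ / [σ√(1−R²)·√(1/10+1/5)] − 1.96), with δ = ln 2 = 0.693 and assumed σ = 0.8.
- R² = 0: 0.693/(0.8 × 0.548) = 1.58, so Φ(−0.38) = 35%.
- R² = 0.2: 1.58/√0.8 = 1.77, so Φ(−0.19) = 42%, a gain of 7 points.
- R² = 0.4: 1.58/√0.6 = 2.04, so Φ(0.08) = 53%, a gain of 18 points.

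This normal approximation ignores ties, the cap and deaths. It confirms the direction only.

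**Step 3: chance imbalance at 10:5.** Let K be the number of patients entering at WHO 5, and x the number of them on placebo. The number of allocations is C(5,x)·C(10,K−x), out of C(15,K).
- K = 4: gaps of at least 30 points occur at x = 0, 3 and 4. (210 + 100 + 5)/1365 = 315/1365 = 23%.
- K = 5: they occur at x = 0, 3, 4 and 5. (252 + 450 + 50 + 1)/3003 = 753/3003 = 25%.

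Neither result includes a gap of exactly 30 points, so neither depends on how the threshold is treated.

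**Step 4: choice of adjusted test.** A van Elteren test stratified by the three scores gained less than rank ANCOVA in most scenarios. It lost power in two weak-link cases (48 → 42 and 32 → 28).

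**The case against.** A plain rank test is a defensible choice for skewed, zero-heavy data at this sample size, and it is valid under randomization. The plan's practice is also mixed. Adjusting a change score for its baseline is routine, the time-to-recovery log-rank test is unadjusted, and the protocol's own row for hospital and ICU stay lists only descriptive statistics. Total oxygen and ventilator days are not listed endpoints in the protocol or in SAP Table 3. Length of hospital stay is listed, but there the link is weakest. Time to room air is already limited to patients on oxygen at baseline. Imbalance would be visible, because SAP Table 6 tabulates baseline scores by arm and SAP Figure 3 splits by baseline scale.

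Deaths can also shrink the gain. The assumed 2/8/20% averages 0.2 × 2 + 0.5 × 8 + 0.3 × 20 = 10.4%, below the 14.9 to 23.5% inpatient fatality cited in protocol 5.8. With 5/15/30% assumed instead, power for oxygen days was about 9% unadjusted and 13 to 14% adjusted.

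All of this stands, and it limits the importance of the point. It does not make the unadjusted test as good: in every scenario run, rank ANCOVA had at least slightly higher power with the type I error held. Seeing an imbalance in a table also does not remove it from the test.

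**Conclusion.** The three comparisons omit an available baseline variable that should predict two of the outcomes, and to a lesser degree the third. If days are halved in 15 patients, adjustment adds about 2 to 5 points of power when the link is weak, and in most of the runs with deaths scored worst case. It adds about 5 to 10 points for a moderate link (15 in one narrower-spread case) and 20 or more only for a strong link. Mostly-zero ventilator days gain less, about 3 to 9 points. The allocation conflict barely changes this. Unadjusted power stayed below about 55% throughout, so the main benefit is precision and protection from chance imbalance.

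A reader might infer that the entry score largely determines these totals, that differences in entry status drown any drug effect, or that the plan forfeits one fixed amount of power. The documents support none of these, because they contain no durations, variances or correlations. The analyses are exploratory, and this is an optional improvement.

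**What to change.** In SAP 8.4.4, 8.4.5 and 8.4.6, make the between-group comparison a Quade rank ANCOVA. Over both arms together, regress the rank of total days on the rank of baseline WHO score as a single linear term. Compare the residuals between arms, with a p-value from permuting the arm labels under the allocation scheme actually used. Keep medians and quartiles by arm, and report the unadjusted Wilcoxon test as a sensitivity analysis. Do not use a van Elteren test stratified by score, since sparse strata at N = 15 can lose power. Make the change before unblinding.

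The cost is three SAP sentences, a few lines of code, one degree of freedom and a slightly less familiar test. No new data are needed.

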8.4.6 Duration of hospitalization (Day 1 - Day 29; measured in days)

The total number of days with recorded use will be the sum of all reported days, regardless of whether the days occur consecutively or in disjoint intervals. Results will be summarized by descriptive statistics including medians and quartiles by treatment arm and compared between treatment groups using Wilcoxon rank sum test.

Summaries of the results of the secondary analyses are displayed in Table 11.

Table 11. COSTA analysis tables - Secondary Analyses.

Table #	Table Name	Table Contents
	Time to recovery, Day 1 - Day 29	Overall and by Treatment group
	Proportion of patients in recovery at Day 60, ITT	Overall and by Treatment group Day 1 – Day 10 Day 1 – Day 60
	Proportion of patients with improvement of one category using the WHO ordinal scale from Day 1, ITT	Overall and by Treatment group Day 1 – Day 10 Day 1 – Day 29
	Proportion of patients with improvement of two categories using the WHO ordinal scale from Day 1, ITT	Overall and by Treatment group Day 1 – Day 10 Day 1 – Day 29
	All-cause mortality, ITT	Overall and by Treatment group At Day 29 At Day 60

Table #	Table Name	Table Contents
	Proportion of patients alive and not in respiratory failure (invasive mechanical ventilation or extracorporeal membrane oxygenation (ECMO) at Day 29, ITT	At Day 90 Overall and by Treatment group Day 1 – Day 10 Day 1 – Day 29
	Summary of the proportion of patients re-hospitalized following initiation of study medication and subsequent discharge (over 60 days), ITT	Overall and by Treatment group
	Duration of hospitalization from Day 1 (Day 1 - Day 29; measured in days), ITT	Overall and by Treatment group
	Change from baseline WHO ordinal scale at Days 10 and 29, ITT	Overall and by Treatment group Baseline – Day 10 Baseline – Day 29
	Total time on supplemental oxygen (Day 1 - Day 29; measured in days), ITT	Overall and by Treatment group
	Total time of non-invasive ventilation or high flow oxygen use (post-dose Day 1 - Day 29; measured in days).	Overall and by Treatment group
	Summary of the proportion of patients with oxygen use at Days 10 and 29, ITT	Overall and by Treatment group
	Summary of the proportion of patients with non-invasive ventilation or high flow oxygen use at Days 10 and 29, ITT	Overall and by Treatment group
	Proportion of patients receiving invasive mechanical ventilation or extracorporeal membrane oxygenation (ECMO, WHO ordinal scale criteria) at Days 10 and 29, ITT	Overall and by Treatment group Day 1 – Day 10 Day 1 – Day 29

8.5 Data Listings

Relevant subject data, including those derived, will be presented in individual subject data listings. All listings will be sorted by treatment regimen, subject number, date/time and visit. Listings will be based on all patients randomized

8.6 Figures

The study specific figures are displayed in Table 12.

Table 12. COSTA Figures.

Figure #	Figure Name
1	Box and whisker plot for each biomarker by treatment group (e.g. marker of NETosis) at day 1, Day 5 and Day 10
2	Kaplan-Meier plot of time to Recovery, by treatment group ITT
3	Histogram of ordinal scores at Day 10 and 29 by treatment group and baseline ordinal scale, ITT.

9 REPORTING CONVENTIONS

P-values will be reported to three decimal places; p-values less than 0.0005 will be reported as "<0.001" and p-values greater than 0.9995 will be reported as ">0.999".

The mean, standard deviation and other statistics will be reported to 1 decimal place greater than the original data. The minimum and maximum will use the same number of decimal places as the original data.

Proportions will be presented as 2 decimal places; values greater than zero but <0.005 will be presented as "<0.01".

Estimated parameters, not on the same scale as raw observations (e.g. regression coefficients) will be reported to 3 significant figures.

10 TECHNICAL DETAILS

Additional summaries/data points may be included in the final version of a table, figure, or listing. Additional tables, figures, and listings may be generated to supplement the planned output.

